### **6.2. Blinding**

Blinding will not be performed to save the patients in aspiration alone group the unnecessary discomfort of blood sampling. We feel this is justifiable as the return of the ganglion or not is a physical finding and not influenced by other factors. The assessor and analyst will be blinded.

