## **SUMMARY**

We propose to undertake a study where we examine the efficacy of Platelet Rich Plasma (PRP) to reduce recurrence in dorsal wrist ganglia (DWG). PRP is produced by centrifugation or spinning of a sample of the patient's blood, which separates out the different components. DWG are cystic collections arising from the wrist joint. Most common treatment is aspiration or reassurance as they have a high recurrence rate with any current treatment.

We will compare aspiration alone and aspiration with injection of PRP. We plan to recruit a maximum of 200 patients. We will assess the efficacy by contacting the patients by email or telephone at 6 weeks and 12 months. Adverse events will be screened for/ managed by a telephone call +/- review as necessary between 7 and 14 days. They will be asked to complete a questionnaire and a Patient Evaluated Measure score (PEMS).

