**2.2. OUTCOMES**

**2.2.1. Primary Outcome**

Presence or absence of ganglion recurrence as reported by the patient at 6 weeks and 12 months.

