**2.2.2. Secondary Outcomes**

Patient reported outcome measure - PEM score which includes patient reported assessments of:

1. Stiffness
2. Pain
3. Cosmesis

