##### **3. Intervention – clinic visit 1 or 2**

- a) Check understanding and continuing desire to participate in study if 2nd visit.
- b) Complete consent form.
- c) Patient fills out a PEM score and demographics collected on SOS.
- d) Randomisation.
- e) If in PRP group 15ml blood sample taken with Arthrex ACP double syringe and processed (see processing instructions in Appendix.9).
- f) Aspiration.
- g) If in PRP group - Injection of PRP (the same volume as aspirated).
- h) Pressure dressing with gauze, wool and crepe for 48 hours.

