##### **4. Adverse event screening/ management**

Patients are offered two options at the treatment visit.

1. Routine review at 10 – 14 days at the clinic  
or
2. Telephone review at 7 days by Miss [name] who will have performed the procedure.

On telephone review if the patient is entirely happy that there are no concerns

then follow up will proceed by email or telephone as below.

If any concerns are raised, or if the patient desires, a face to face review will be arranged ideally within 24 hours but no longer than 72 hours. Recurrence or other outcomes will not be assessed at this time.

5. SOS/ Email/ Telephone interview - 1 (6 weeks)
  - a) Ganglion questionnaire
  - b) PEM score
  - c) Note any adverse events
  
6. SOS/ Email /Telephone interview - 2 (12 months)
  - a) Ganglion questionnaire
  - b) PEM score
  - c) Note any adverse events

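### Section 6.2 claims a blinded assessor, but recurrence and the PEM score are judged by patients who can tell their arm, so the claim can cover at most the staff who take down the answers

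*Combined protocol and SAP*

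**What the plan says.** Section 6.2 makes three statements. Patients will not be blinded, so that the aspiration-only arm is spared a blood draw. The reason this is thought acceptable is: "We feel this is justifiable as the return of the ganglion or not is a physical finding and not influenced by other factors". Then: "The assessor and analyst will be blinded".

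Section 2.2.1 defines the primary outcome as: "Presence or absence of ganglion recurrence as reported by the patient at 6 weeks and 12 months". Section 2.2.2 describes the secondary outcome in similar terms: "Patient reported outcome measure - PEM score which includes patient reported assessments of" stiffness, pain and cosmesis.

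On collection, the Summary states: "We will assess the efficacy by contacting the patients by email or telephone at 6 weeks and 12 months". Section 3.1 lists the first outcome contact as "SOS/ Email/ Telephone interview - 1 (6 weeks") and gives the 12-month contact in the same form. The early review in Section 3.1 is for adverse events, and of it the plan says: "Recurrence or other outcomes will not be assessed at this time".

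On how the arms differ, Section 3.1 has: "If in PRP group 15ml blood sample taken with Arthrex ACP double syringe and processed", followed in that arm by an injection after the aspiration.

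**The concern.** The defence in Section 6.2 would suit an endpoint read by an examiner or by imaging. The endpoint in Section 2.2.1 is an answer given by a person who knows whether PRP was injected. The blinding sentence names an assessor, but for both outcomes the person making the judgement is the patient, whom the same paragraph leaves unblinded.

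The consequence is a wrong description of the evidence. A report could cite the protocol and call the trial assessor-blinded, and readers would credit the primary outcome and PEM score with a protection that neither has. If patients' answers depend on their arm, the comparison could be pushed towards PRP or away from it. Section 10.2 plans nothing that would show how much of this the result could withstand.

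**Working it through.** **1. The sections side by side**

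| Question | Where | Answer |
|---|---|---|
| Who judges recurrence? | 2.2.1 | The patient |
| Who judges the PEM score? | 2.2.2 | The patient |
| Is the patient blinded? | 6.2 | No |
| Can the patient tell the arm? | 3.1 | Yes: only PRP patients have blood drawn and an injection |
| Does anyone examine for recurrence? | 3.1, Summary | Not in the visible schedule; the early review excludes it |
| Who is the assessor? | 6.2 | Not defined |

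Section 4.3 mentions attendance at follow-up visits and Section 14.3 defines study end by a last visit, but neither describes an examination. The sentence in 6.2 can therefore apply only to people who take or record answers.

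**2. The plan's own sample size reproduces**

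Inputs (10.1, 10.2): 59% v 34%, 90% power, alpha 0.05, taken as two-sided because sidedness is not stated.

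- Mean proportion = (0.59 + 0.34)/2 = 0.465.
- n = [1.96·√(2 × 0.465 × 0.535) + 1.2816·√(0.59 × 0.41 + 0.34 × 0.66)]² / 0.25² = 81.55.
- With continuity correction: (81.55/4)·[1 + √(1 + 4/(81.55 × 0.25))]² = 89.37, so 90 per arm.
- With dropout: 90/0.9 = 100.

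These match the plan. The sample size is not in dispute; it supplies the setting for what follows.

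**3. Illustration: what differential reporting could do to the primary outcome**

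Every misreporting rate here is an assumption. The method sums exact binomial probabilities over all outcomes with 90 per arm, for one chi-squared test at 0.05, ignoring the early looks in 10.1. Section 10.2 allows the test with or without continuity correction, so both are shown. Control patients are assumed to report accurately.

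No true effect, with a fraction m of PRP recurrences unreported; the reported PRP rate is 0.59 × (1 − m):

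| m | Reported PRP rate | Significant, uncorrected | Significant, corrected |
|---|---|---|---|
| 0 | 0.590 | 5.1% | 3.6% |
| 5% | 0.5605 | 6.8% | 5.0% |
| 10% | 0.531 | 12.1% | 9.4% |
| 15% | 0.5015 | 21.2% | 17.3% |

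Opposite direction: true rates 59% v 34%, and 10% of recurrence-free PRP patients report a recurrence. The reported PRP rate is 0.34 + 0.66 × 0.10 = 0.406. Power falls from 92.0% / 89.5% to 68.2% / 62.7% (uncorrected / corrected).

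**4. Tipping points**

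Take 53/90 recurrences in the control arm (0.59 × 90 = 53.1). Add k unreported recurrences to the PRP count until significance at 0.05 (chi-squared 3.841) is lost.

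- Uncorrected, lost at 40: 180 × (53 × 50 − 37 × 40)² / (90 × 90 × 93 × 87) = 3.76.
- Corrected, lost at 39: 180 × (53 × 51 − 37 × 39 − 90)² / (90 × 90 × 92 × 88) = 3.76.

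The share is k divided by the true PRP count.

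| Reported PRP count | k, uncorrected | k, corrected |
|---|---|---|
| 31 (0.34 × 90 = 30.6, the design effect) | 9 (9/40 = 22.5%) | 8 (8/39 = 20.5%) |
| 34 (p = 0.005 / 0.007) | 6 (6/40 = 15.0%) | 5 (5/39 = 12.8%) |
| 38 (p = 0.025 / 0.037) | 2 (2/40 = 5.0%) | 1 (1/39 = 2.6%) |

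**5. PEM score**

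Two-sided t test, 90 per arm, 178 degrees of freedom, no true effect, assumed reporting shift of d standard deviations between arms; noncentrality = d·√(90/2) = d·√45. For d = 0, 0.1, 0.2 and 0.3 the false-positive rate is 5.0%, 10.2%, 26.6% and 51.7%. Nothing in the documents indicates which d, if any, is realistic.

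**The case against.** The strongest reply is that nothing is hidden. Section 6.2 opens by saying that blinding will not be performed, and Section 2.2.1 says who reports recurrence. That stands: a reader who inferred concealment would be wrong. The fault is an inaccurate claim and a rationale that does not fit the outcome.

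Second, the word assessor may have a real meaning. A telephone interviewer who does not know the arm is less likely to lead the patient or record selectively. The questionnaire, case report forms, flow diagram, steering committee charter and delegation log are not visible and may name that person. This stands as a reason to define the role. It does not rescue the sentence for the outcomes themselves, because no such document could blind the patient's own report.

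Third, a reader might infer from Sections 6.1 and 11.2 that the people handling follow-up are in fact unblinded. The person who makes the envelopes also oversees compliance with follow-up, and an orthopaedic registrar, the role that performs the procedures (Section 7), is among those who check the forms. The documents do not support that inference. Overseeing compliance is not taking answers, checking forms is not assessing outcome, and with names removed the registrars cannot be matched. These sections show only that the assessor is not identified.

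Fourth, the error rates describe misreporting in an open design that this review would keep, so they do not measure the effect of the sentence in 6.2. That is correct. It is also fair that 5% non-reporting leaves the error rate near nominal, that the design effect is fairly robust, and that the 38/90 case is fragile as any barely significant result would be.

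Finally, one might answer that patients can usually see a returning lump. That may limit the problem, but no section says so, and it should not be written into the protocol as fact.

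**Conclusion.** The point holds in a limited form. For the primary outcome and the PEM score the judgement belongs to unblinded patients, so the statement that the assessor is blinded cannot be true of the outcome judgement. The claim that recurrence is free of other influences does not fit a self-reported endpoint with no examination in the visible schedule. This rests on the current text and on the inference, from the visible difference in procedures, that patients know their arm.

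The size of any bias is unknown. The figures above show sensitivity on assumed rates: 10% one-sided non-reporting with no true effect gives 12.1% / 9.4% false positives, while the planned effect would need 9 / 8 hidden recurrences to lose significance. A reader might infer that the trial is biased in favour of PRP. The documents do not support that, since misreporting could equally mask a benefit. The trial remains usable as an open, patient-reported comparison and should be described as one. The plan should be corrected.

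**What to change.** Keep the open design and the blinded analyst.

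**Section 6.2.** Delete the closing clause of the second sentence, which denies any other influence on recurrence. Replace the last sentence with:

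> The primary outcome and PEM score are self-reported by participants who are not blinded, and reports may be influenced by knowledge of allocation. Where answers are taken by telephone, they will be taken by an existing team member who did not treat the patient and does not hold the allocation list; participants will be asked not to reveal their treatment, and any unblinding will be recorded. The analyst will be blinded.

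Do not add a statement that recurrence is usually visible to the patient.

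**Reporting.** Describe conclusions as unblinded patient-reported recurrence, not as assessor-blinded.

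**Section 10.2.** Add a tipping-point sensitivity analysis giving the number of differentially misreported recurrences that would overturn the result. Run it at each time point for which a primary-outcome result is reported, using the same chi-squared version as that result. It describes robustness and does not remove bias.

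**Cost.** The stated blinding becomes less favourable, an existing team member must be assigned to telephone follow-up, and there is one extra analysis on data already collected. Section 14.1 requires sponsor, REC and NHS R&D approval before the amendment is used.

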### **6.3. Withdrawal Procedures**

A patient may withdraw from the trial at any time. A withdrawal form will be completed and filed in the trial folder. If the patient grants permission at the time of withdrawal data will be retained for inclusion in analysis as appropriate. Patients will be replaced if they have not completed either follow up time points.

**7.****STUDY AND SAFETY ASSESSMENTS**

No specific safety requirements are required PRP is already commonly used for injections and as a product generated from the patient's own blood has an excellent safety profile. Blood will be sampled, processed and re-injected by the same person in the same visit, with only one patient at a time receiving the intervention to ensure no mistakes regarding patient identity can be made.

The sample is taken, processed and injected from the same specially designed syringe so that the internal contents maintain sterility. This is routinely performed in the out-patient clinic setting rather than theatre, although every effort at sterility will be maintained with sterile dressing packs, gloves and dressings being used. All the procedures will be performed by Miss [name] who has been trained in venepuncture and aspiration of ganglia via her role as orthopaedic registrar and has undertaken additional training from Nursing/ Medical Staff trained and practiced at processing the samples at the Orthopaedic Out-patient clinic.

Adverse Events (AE) anticipated may include localised minor pain or swelling of short duration (24-72hrs), minor cellulitis requiring oral antibiotics treated by GP.

The patients will be offered clinical or telephone review (which may proceed to urgent clinical review if concerns to monitor for the presence of adverse events and to ensure they are recognised and treated promptly. The patient information leaflet contains instructions on when and where to seek medical help if concerns at any time. Patient reports will be requested at each follow up with space for recording on each CRF. The patients will also be able to inform the study of AE on SOS. Finally, the GP will be advised to inform [name] of any study related patient contact with them. Clinic follow up by [name] or his registrar will be arranged as required. As a new indication for PRP we plan to collate and report on all AE.

Serious Adverse Events (SAE) such as hospitalisation for major cellulitis requiring IV antibiotics, abscess formation or septic arthritis requiring surgical management will be reported immediately to the sponsor. These are anticipated to be rare events (<1%) in line with major infective complications from other Orthopaedic procedures.

Upon recognition of any event an Adverse event an Adverse Event Form should be completed and placed in the study file. The file will also contain an AE log.

## **8. DATA COLLECTION AND MANAGEMENT**

### **8.1. Data Collection**

Data will be collected as both electronic files and paper questionnaires and letters. Electronic files will be collected with the Surgical Outcomes System, a research registry run by Arthrex. All data will be kept secure and confidential, see appendix 11. Paper files will be kept in a locker filing cabinet in the Upper Limb Unit Secretaries office.

All participants will be assigned a unique identifier for the duration of the study. A separate log will be kept linking the ID number to the participant which will be kept and stored confidentially.

Surgical outcome system is an online bespoke database containing the data as shown on the case report forms in Appendix 6 and 7. Patients will be identified only by their unique study ID and demographic information (age at time of study and sex) will be entered. Access is password protected on an individual basis. The database is a Microsoft SQL Server database using transparent data encryption. Plausibility data validation is in place, data is checked upon saving. There is a daily full back up of the data. Data enquires will be handled by Miss [name].

SOS is hosted on servers operated exclusively for Arthrex by Amazon Web Services, Inc. (AWS). The data will be stored on an AWS Server in Germany. The data centre has multiple layers of operational and physical security to ensure the integrity and safety of the data. The data centre utilizes state-of-the-art electronic surveillance and multi-factor access control systems. The data centre is staffed 24 / 7 by trained security guards and access is authorized on a least privileged basis. See also appendix 11. An anonymised database will be stored on secure shared NHS Grampian drive, with access only to research team.

Data files from SOS will be extracted onto NHS computers as password protected excel files will be stored on secure shared NHS Grampian drive, with access only to research team.

**9. LABS AND SAMPLE ANALYSIS**

**9.1.** There is no laboratory requirement. Blood samples will be processed by centrifuge (spinning) in the clinic to produce PRP with sterile technique. No further analysis or storage will be undertaken. Any remaining blood products will be safely disposed of in the clinic.

**10. STATISTICS AND DATA ANALYSIS**

**10.1. Sample Size Calculation**

90 participants in each arm would give a 90% power to detect a change in recurrence rate of 25%. We believe this is adequate as current recurrence rates are 59%. This would need to be increased to 100 participants recruited per arm to allow for 10% drop out from follow-up.

As the recurrent rate is so large recruiting 90 patients would detect up to a 25% difference in recurrence rate. To ensure the trial is not extended beyond the point of answering our question we have also calculated numbers to allow for the trial to be closed early if we have sufficient data.

62 participants completing follow-up in each arm would give 90% power to detect a change in recurrence rate of 30%. This would need to be increased to 69 per arm to allow for 10% drop out from follow-up.

46 participants completing follow-up in each arm would give 90% power to detect a change in recurrence rate of 35%. This would need to be increased to 51 per arm to allow for 10% drop out from follow-up.

Therefore we will undertake initial data analysis after 51 and 69 participants have completed their 6 week review and if the difference in the recurrence rate is more than 35% or 30% then we will conclude the trial, but all outstanding follow up will be completed and data included in final analysis.

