## **1.2. Rationale for Study**

We believe that by injecting platelet rich plasma into ganglia after aspiration of the contents, the platelets would be activated by exposure to the collagen wall and adherent clot would form in the cavity. It is plausible that the growth factors would cause differentiation of the mesenchymal cells within the walls and draw in inflammatory cells and thus from a relatively acellular position the means for healing have been provided. If the walls became scarred together obliterating the space then recurrence would be reduced. Aspiration is commonly performed and we do not believe any additional risk is posed to the patient from injection of PRP. Ganglia usually recur by 6 months so 1 year is adequate follow up.

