**10.2. Proposed Analysis**

Statistical analysis will be performed to assess homogeneity of the study groups and efficacy of treatment. The primary outcome will use chi-squared test (with or without continuity correction). The secondary outcome will be assessed using independent T test if normally distributed or Mann-Whitney test if not.

The difference between the two groups will be significant if the p values are less than 0.05.

The analysis will be performed by [name] who is a Clinical Specialist on the Arthrex Research team based in Germany.

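### Section 10.1 closes recruitment on the 6-week recurrence difference without showing that it is a guide to 12 months

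*Combined protocol and SAP*

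**What the plan says.** Section 10.1 gives three sample sizes at 90% power: "90 participants in each arm would give a 90% power to detect a change in recurrence rate of 25" per cent, "62 participants completing follow-up in each arm would give 90% power to detect a change in recurrence rate of 30" per cent, and "46 participants completing follow-up in each arm would give 90% power to detect a change in recurrence rate of 35" per cent. With 10% dropout these become 100, 69 and 51 per arm. The baseline is stated without a time point: "We believe this is adequate as current recurrence rates are 59" per cent.

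The early-closure rule in the same section, applied at 51 and at 69 participants, reads: "completed their 6 week review and if the difference in the recurrence rate is more than 35% or 30% then we will conclude the trial". Patients already enrolled are still followed up and enter the final analysis, so closure ends recruitment and not 12-month data collection.

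Section 2.2.1 makes patient-reported recurrence at 6 weeks and at 12 months the primary outcome, without ranking the two. Section 1.2 justifies the length of follow-up: "Ganglia usually recur by 6 months so 1 year is adequate follow up".

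**The concern.** The 35- and 30-point thresholds are the effects for which 46 and 62 completers per arm were sized, from a 59% recurrence rate. The rule applies them at the first of two outcome contacts, well before the 6 months by which Section 1.2 expects most recurrences to have appeared. No section gives the recurrence rate expected at 6 weeks, or argues that a difference then will still be there at 12 months.

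The primary objective in Section 2.1.1 is whether PRP prevents recurrence. A 6-week difference cannot tell prevention from delay. If recruitment stops on an early difference that later shrinks, the 12-month comparison has to be made with a smaller trial than planned. Finishing outstanding follow-up shows the 12-month result but adds no patients.

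**Working it through.** **1. Where the thresholds come from.** Inputs: 59% recurrence and differences *d* of 25, 30 and 35 points (Section 10.1); significance level 0.05 and a chi-squared test with optional continuity correction (Section 10.2). Two-sided testing is assumed because it reproduces the stated numbers.

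Uncorrected: n0 = [1.960·√(2p̄(1−p̄)) + 1.282·√(p1(1−p1) + p2(1−p2))]² / d². Corrected: n = (n0/4)·[1 + √(1 + 4/(n0·d))]².

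For 59% v 24%: p̄ = 0.415, n0 = 39.5, n = 45.1, rounded up to 46. The same steps give 62 for 30 points and 90 for 25. All three stated sizes are reproduced. Dividing by 0.9 gives 51.1, 68.9 and 100, against the stated 51, 69 and 100. The sample sizes are sound; the thresholds belong with a 59% control rate.

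**2. What the rule needs at 6 weeks.** To exceed 35 points the aspiration arm must show more than 35% recurrence, even if the PRP arm shows none. If 59% is the rate at full follow-up (an inference), that is 35/59 = 59% of its eventual recurrences; for 30 points it is 30/59 = 51%.

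**3. How often the rule fires.** The share of recurrences visible at 6 weeks is not in the documents. Assume it is equal in both arms and vary it. The chance of crossing at either look (binomial), for true full-follow-up rates of 59% v 24%, is:

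| Share visible at 6 weeks | 6-week rates | Looks at 51 and 69 per arm | Looks at 51 and 69 in total |
|---|---|---|---|
| Half | 29.5% v 12% | 4% | about 10% |
| Three quarters | 44.25% v 18% | 34% | about 40% |
| All | 59% v 24% | 77% | about 72% |

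Both readings are shown because the closure sentence does not say whether 51 and 69 are per arm. The totals column takes 26 and 25, then 35 and 34.

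**4. If it fires on a difference that partly fades.** Assume 45% v 10% at 6 weeks and 59% v 34% at 12 months. With looks per arm, closure is 54% at the first look and about 79% at either (about 72% if totals).

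Power of a 12-month comparison of 59% v 34% (uncorrected chi-squared, exact enumeration):

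- 46 evaluable per arm (51 × 0.9, first look): 67%
- 62 per arm (69 × 0.9, second look): 82%
- 90 per arm (full design): 92%

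For 20 points (59% v 39%) it is 48% at 46 per arm against 76% at 90. The sizes of 46 and 62 are floors under the per-arm reading, because patients enrolled while the 6-week data mature also count. The documents give no recruitment rate from which to size that addition.

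**5. A limit on step 4.** Those powers are for a trial of the given size; they do not condition on closure having happened. Trials that close are those with a favourable 6-week difference. If a ganglion reported as recurred at 6 weeks also counts at 12 months (assumption), then (59−45)/(100−45) = 25.5% of those still clear recur later in the aspiration arm and (34−10)/(100−10) = 26.7% in the PRP arm. Simulating this (400,000 trials, no extra enrolment) gives power of about 84% in trials closed at the first look, 83% at the second and 79% in those that run on. Overall: 0.536×0.84 + 0.250×0.83 + 0.214×0.79 = 0.83, against 0.92 with no rule. The loss remains, but averaged over all trials it is smaller than 67% against 92% suggests.

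**The case against.** Several points on the other side stand.

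- **Six weeks is a declared primary time point.** A reader might infer that the rule uses the wrong outcome. Section 2.2.1 does not support that. What is missing is a reason to let the earlier time point decide whether recruitment continues.
- **The 59% has no time point.** A reader might take it as a 12-month rate. That is a reasonable inference from the one-year follow-up, but the protocol does not say so.
- **The rule is not shown to be unreachable.** Section 1.2 gives a time by which ganglia usually recur, which is an upper limit and not an accrual curve. If recurrences accrued evenly over 26 weeks, the 6-week control rate would be 0.59 × 6/26 = 13.6% and closure would be well under 1%; but nothing in the documents supports even accrual. If most recurrences appear early and the difference lasts, the rule does its job: 59% v 24% has about 93% power with 46 per arm.
- **A rule that never fires does no harm to validity.** The trial then recruits the planned 200.
- **Nothing says that PRP only delays recurrence.** Section 1.2 proposes that the cavity is obliterated. The 45% v 10% case is an illustration, with 45/59 = 76% of control recurrences already visible.
- **Closure by chance is rare.** With no true 6-week difference, crossing in favour of PRP at either look is about 0.03% with looks per arm and at most about 0.9% if totals.

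Completing follow-up after closure is a real safeguard, since a fading effect would be seen, though with less precision.

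**Conclusion.** The concern holds as one of timing and durability. The closure thresholds were sized on a 59% recurrence rate and on completed follow-up, but they are applied at 6 weeks with no expected rate and no argument that a 6-week difference predicts 12 months.

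The consequence runs one way. If the rule seldom fires, only a chance to stop early is lost. If it fires on a difference that partly fades, the 12-month comparison is left smaller than planned, to the extent shown in steps 4 and 5. Those figures rest on assumed 6-week rates, the per-arm reading of 51 and 69, 10% dropout and no credit for patients enrolled during the wait. The documents do not establish that the rule is almost unreachable, that it uses a non-primary outcome, or that PRP merely delays recurrence.

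This should be fixed, with moderate confidence: the mismatch is in the text, but its size depends on an early-recurrence share that the protocol does not give.

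**What to change.** In Section 10.1, either apply the 35- and 30-point early-closure thresholds to recurrence at the 12-month contact, or delete the early-closure rule and recruit to the planned maximum of 200.

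The edit is one sentence and leaves the maximum unchanged. The cost of the first option is delay: 12-month data arrive late, so early closure would save few patients. If the 59% does describe 12 months, the thresholds applied there (51 and 69 per arm) would be crossed at either look in about 31%, 54% and 77% of trials for true differences of 25, 30 and 35 points. The second option gives up early closure and keeps the full 12-month power. The change should be made before the first look, because recruitment closed on 6-week data is hard to reopen.

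### The early-closure rule in Section 10.1 reuses the design differences (35 and 30 points) as thresholds for the observed difference, so at the look sized for each effect it closes the trial only about half the time, not 90%.

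*Combined protocol and SAP*

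**What the plan says.** Section 10.1 (Sample Size Calculation) takes a control recurrence rate from the statement "We believe this is adequate as current recurrence rates are 59"%. It gives three sizes:

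- "90 participants in each arm would give a 90% power to detect a change in recurrence rate of 25"%
- "62 participants completing follow-up in each arm would give 90% power to detect a change in recurrence rate of 30"%
- "46 participants completing follow-up in each arm would give 90% power to detect a change in recurrence rate of 35"%

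The two smaller sizes exist to allow early closure. The stated purpose is "To ensure the trial is not extended beyond the point of answering our question". They are inflated for dropout to 69 and 51 per arm. The paragraph that follows opens with *Therefore*. It places looks after 51 and 69 participants have had their 6-week review, without saying per arm or in total, and sets the rule: "if the difference in the recurrence rate is more than 35% or 30% then we will conclude the trial".

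Section 10.2 (Proposed Analysis) gives the only significance criterion, "The difference between the two groups will be significant if the p values are less than 0.05", for a chi-squared test with or without continuity correction. Neither section gives an interim p-value boundary.

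**The concern.** Power is the probability that a test reaches significance when the true difference has a given value. It is not the probability that the observed difference exceeds that true value. An observed difference scatters around the true one, so it lies above it about half the time. A rule that requires the observed difference to exceed 35 points, at a look sized for a true 35 points, therefore cannot inherit the 90% quoted for that size.

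What is at stake is the section's own aim of not running on once the question is answered. At 46 per arm an observed difference of 30 points would be well beyond p<0.05, yet the trial would continue. A raw-difference hurdle set this high also tends to be crossed when the estimate is exaggerated.

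**Working it through.** **Inputs.** Control rate 59%; differences of 25, 30 and 35 points, read as absolute; 90% power; 10% dropout; thresholds above 35 points at the first look and above 30 at the second (all Section 10.1). Alpha 0.05 and chi-squared test (Section 10.2). 1:1 allocation (Section 6.1). Two-sided testing is an assumption; it reproduces the plan's sizes.

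**Step 1: reproduce the sizes.** With p1 = 0.59, p2 = p1 − d and p̄ their mean:

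n = [1.96·√(2p̄(1−p̄)) + 1.2816·√(p1(1−p1) + p2(1−p2))]² / d²

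n with continuity correction = (n/4)·[1 + √(1 + 4/(n·d))]²

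| d | p2 | n | n corrected | plan | plan ÷ 0.9 |
|---|---|---|---|---|---|
| 0.25 | 0.34 | 81.6 | 89.4 | 90 | 100 |
| 0.30 | 0.29 | 55.4 | 61.9 | 62 | 68.9 |
| 0.35 | 0.24 | 39.5 | 45.1 | 46 | 51.1 |

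The plan's sizes are those of a two-sided 5% test with continuity correction.

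**Step 2: what the 90% refers to.** The observed difference needed for p<0.05 is 1.96·√(2p̄(1−p̄)/n), plus 1/n with the correction.

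- 46 per arm: 1.96 × 0.1027 = 20.1 points; corrected, 22.3. In whole patients, uncorrected, every difference of 10/46 = 21.7 points or more is significant.
- 62 per arm: 1.96 × 0.0892 = 17.5 points; corrected, 19.1. In whole patients, uncorrected, 11/62 = 17.7 points.

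At a true 35 points the standard error at 46 per arm is √((0.59·0.41 + 0.24·0.76)/46) = 0.0960. The chance of passing 22.3 points is Φ((0.350 − 0.223)/0.0960) = Φ(1.32) = 0.91. This is the plan's 90%.

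**Step 3: what the rule requires.** The hurdle is 35 points, so the same calculation gives Φ((0.35 − 0.35)/0.0960) = Φ(0) = 0.50. Exact binomial enumeration gives 0.47, because 16/46 = 34.8 points fails and 17/46 = 37.0 passes. At 62 per arm and a true 30 points it gives 0.51. An observed difference equal to the hurdle has z = 0.35/0.1027 = 3.41 (p about 0.0007) or 0.30/0.0892 = 3.36 (p about 0.0008), uncorrected. At 51 and 69 per arm the p-values are about 0.0003 and 0.0004.

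**Step 4: the rule over both looks** (simulation, 400,000 trials per setting, control 59%):

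| | 46/62 per arm | 51/69 per arm | 51/69 as totals (25/34 per arm) |
|---|---|---|---|
| True 35, look 1 | 47% | 53% | 54% |
| True 30, look 2 alone | 51% | 52% | 47% |
| True 35, by look 2 | 74% | 77% | 69% |
| True 30, by look 2 | 52% | 54% | 52% |
| True 25, by look 2 | 30% | 30% | 36% |
| No difference, either look | 0.1% | 0.06% | 1.8% |

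If the odd patient in each total is kept (25 and 26, then 34 and 35), the three cumulative figures in the last column become about 72%, 56% and 39%. The per-arm figures at the matching look stay within 0.46-0.54 for control rates from 40% to 93%.

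**Step 5: side effects.** Counting closure or a final uncorrected p<0.05 at 90 per arm as a positive result, type I error is about 5.2% with or without the rule for 46/62 per arm. It is about 6.0-6.5% if the counts are totals. Power at 25 points is 92% with or without the rule (46/62 per arm, uncorrected test). At a true 25 points the mean observed difference at closure is 37 points.

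**The case against.** The strongest reply is that Section 10.1 never promises a 90% chance of closing early. It attaches 90% to sample sizes, and *Therefore* can be read as introducing when to look. A demanding interim hurdle is a respectable choice, since any alpha-controlled boundary is stricter than p<0.05. Nor does an alpha-spending boundary reach 90% at the matching looks. This stands in part: strictness is not the defect. But the section does not present the hurdle as deliberately strict. It takes 35 and 30 directly from the power statements.

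A reader might infer that the whole rule closes only about half the time at every effect for which 90% is quoted. The documents do not support that. The second look raises closure at 35 points to 74-77%. The 90% for 25 points belongs to the full 90 per arm, not to a look. Only at 30 points is the cumulative figure about half.

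A reader might also infer serious type I inflation or a lost trial. Neither follows. With per-arm looks the null chance of crossing is about 0.1%, and a missed threshold only means that recruitment goes on to 100 per arm. The 37-point figure is the estimate at closure; Section 10.1 completes outstanding follow-up and includes it in the final analysis, though this does not remove the selection.

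**Conclusion.** The point holds for each look taken with the effect it was sized for: closure is 47-54% at 35 points and 47-52% at 30 points, where the sizing rests on 90%. Cumulatively the shortfall is smaller at 35 points (74-77%; 69% if totals) and remains at 30 points (52-54%). The thresholds are wrongly derived and work against the section's aim of stopping once the question is answered. The consequence is modest: early closure happens less often than the sizing suggests, with no loss of the final analysis. This should be corrected, but it does not undermine the trial.

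The figures assume absolute differences, 35 applied at the first look and 30 at the second, and a 59% control rate in the 6-week data. If more than 30 points sufficed at the first look as well, closure there at a true 35 points would be 70-72%.

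**What to change.** First settle three things in Sections 10.1 and 10.2: that the looks are counted per arm, and in completers; which time point is primary, since Section 2.2.1 names both 6 weeks and 12 months; and which version of the chi-squared test applies. If 12 months is chosen, 6-week looks do not inform the boundary for that outcome.

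Then replace the raw-difference thresholds with an alpha-spending p-value boundary computed at the actual information fractions. For looks at 46 and 62 and a final analysis at 90 completers per arm (fractions 0.511, 0.689, 1), a Lan-DeMets O'Brien-Fleming-type boundary has z of about 2.93, 2.49 and 2.00: close if p<0.0034 or p<0.013, with a final test at p<0.046 (rounded).

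| | Uncorrected | Continuity-corrected |
|---|---|---|
| Close at look 1, true 35 | 72% | 63% |
| Close by look 2, true 30 | 84% | 79% |
| Overall power, true 25 | 92% | 89% |

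The cost is a few sentences and a slightly stricter final level (about 0.046 instead of 0.05). Exaggeration at closure is reduced, not removed: the mean is 31 points instead of 37 when the truth is 25 (uncorrected test).

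If 51 and 69 are totals, the boundary must be recomputed and no gain in closing probability should be claimed. Even the boundary above would close less often at the first look than the present rule.

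Alternatively, keep the thresholds as a deliberately strict rule, remove the link to 90% power, and state the closing probabilities per look and cumulatively. For 46/62 per arm these are 47% then 74% at 35 points, and 28% then 52% at 30 points.
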